6.5 VACCINATION VISITS (VISITS 1-4)

6.5.1 Procedures for Visit 1

- Ask if any medications have been started or stopped since the last visit
- Urine pregnancy test prior to vaccination
- Measure height and weight to determine BMI
- Take vital signs prior to injection
- Blood will be drawn for:
 - Immunomonitoring and other analyses (eight 10.0 mL rubber green top sodium heparin tubes unless pregnant then draw only 2 tubes)
 - CBC (to be performed in UAMS clinical laboratory)
 - CMP (to be performed in UAMS clinical laboratory)
- Administer vaccination injection
- Repeat vital signs after at least 30 min has passed since the injection
- Monitor for any immediate adverse reactions
- Offer dose of ibuprofen or naproxen
- Hand out “Subject Diary” and ask the subject to fill it out and bring it back at the next visit

6.5.2 Procedures for Visit 2

- Ask for the filled out “Subject Diary”. If the subject did not return it, ask “Have you experienced any side effects since the last injection?”
- Ask if any medications have been started or stopped since the last visit
- Urine pregnancy test prior to vaccination
- Take vital signs prior to injection
- Blood will be drawn for
 - Immunomonitoring and other analyses (eight 10.0 mL rubber green top sodium heparin tubes unless pregnant then draw only 2 tubes)
- Administer vaccination injection
- Repeat vital signs after at least 30 min has passed since the injection
- Monitor for any immediate adverse reactions
- Offer dose of ibuprofen or naproxen
- Hand out “Subject Diary” and ask the subject to fill it out and bring it back at the next visit

6.5.3 Procedures for Visit 3

- Ask for the filled out “Subject Diary”. If the subject did not return it, ask “Have you experienced any side effects since the last injection?”
- Ask if any medications have been started or stopped since the last visit
- Urine pregnancy test prior to vaccination
- Take vital signs prior to injection
- Blood will be drawn for:
 - Immunomonitoring and other analyses (eight 10.0 mL rubber green top sodium heparin tubes unless pregnant then draw only 2 tubes)
 - CBC (to be performed in UAMS clinical laboratory)
 - CMP (to be performed in UAMS clinical laboratory)
- Administer vaccination injection
- Repeat vital signs after at least 30 min has passed since the injection
- Offer dose of ibuprofen or naproxen
- Monitor for any immediate adverse reactions
- Hand out “Subject Diary” and ask the subject to fill it out and bring it back at the next visit

6.5.4 Procedures for Visit 4

- Ask for the filled out “Subject Diary”. If the subject did not return it, ask “Have you experienced any side effects since the last injection?”
- Ask if any medications have been started or stopped since the last visit
- Urine pregnancy test prior to vaccination
- Take vital signs prior to injection
- Blood will be drawn for:
 - Immunomonitoring and other analyses (eight 10.0 mL rubber green top sodium heparin tubes unless pregnant then draw only 2 tubes)
 - Administer vaccination injection
 - Repeat vital signs after at least 30 min has passed since the injection
 - Monitor for any immediate adverse reactions
 - Offer dose of ibuprofen or naproxen
 - Hand out “Subject Diary” and ask the subject to fill it out and bring it back at the next visit

6.6 Interim Contraceptive Use Reminder Letter

6.6.1 Procedure: Mail the Reminder Letter to the subject after vaccination 4

6.7 6-MONTH VISIT

The 6-Month Visit will be scheduled about six months (\pm 2 weeks) after Vaccination Visit 4.

6.7.1 Procedures for 6-Month Visit

- Perform a physical examination
 - Obtain vital signs
 - Blood pressure

- Heart rate
- Respiratory rate
- Temperature
- Weight
- Ask if any medications have been started or stopped since last visit
- Perform colposcopy
 - Obtain ThinPrep for Pap smear, HPV-DNA and bacterial testing
 - Record the lesion(s), locations on the cervix, image cervix using the colposcope-mounted image capture system (if available)
 - Record in how many cervical quadrants the lesions are visible
- Colposcopy may be performed in the OR if medically necessary. A COVID-19 test may be required per hospital policy prior to intervention in the OR.
- If determined to be necessary by the physician (ONLY in cases where there is a suspicion of progressive disease), obtain punch biopsy and endocervical curettage
- Blood will be drawn for:
 - Immunomonitoring and other analyses (eight 10.0 mL rubber green top sodium heparin tubes unless pregnant then draw only 2 tubes)
 - CBC (to be performed in UAMS clinical laboratory)
 - CMP (be performed in UAMS clinical laboratory)
- If Pap smear and/or biopsy results are suspicious for or consistent with HSIL and if the subject decides not to return for the 12-Month Visit, the optional LEEP visit may be offered as long as a study physician determines doing so would be beneficial.
- If a cervical cancer diagnosis is confirmed prior to being withdrawn from the study, the subject may be offered a hysterectomy if a study physician determines it to be medically necessary.

6.8 Interim Contraceptive Use Reminder Letter

6.8.1 Procedure: Mail the reminder letter after the 6-month visit

6.9 12-MONTH VISIT

The 12-Month Visit will be scheduled approximately six months (\pm 2 weeks) after the 6-Month Visit.

6.9.1 Procedures for 12-Month Visit

- Perform a physical examination
 - Obtain vital signs
 - Blood pressure
 - Heart rate
 - Respiratory rate
 - Temperature
 - Weight
 - Ask if any medications have been started or stopped since last visit
- Perform colposcopy
 - Obtain ThinPrep for HPV-DNA and bacterial testing

- Record the lesion(s), locations on the cervix, image cervix using the colposcope-mounted image capture system (if available)
- Record in how many cervical quadrants the lesions are visible
- Obtain at least one punch biopsy from each of the 4 quadrants and possibly endocervical curettage (these biopsies will be evaluated by 2 pathologists who are blinded to each other's diagnosis, and consensus will be reached in case of non-concordant initial interpretations)
 - Obtain at least one biopsy from each quadrant with visible lesions
 - In a quadrant without visible lesions, obtain at least one biopsy from each quadrant described to have had HSIL lesions at the Screening Visit
 - In a quadrant without visible lesions and without a record of having had HSIL lesions at the Screening Visit, obtain one blind biopsy
- Colposcopy may be performed in the OR if medically necessary. A COVID-19 test may be required per hospital policy prior to intervention in the OR.
 - ECC is required at 12 month visit if the entire squamocolumnar junction is not visualized
- Blood will be drawn for:
 - Immunomonitoring and other analyses (eight 10.0 mL rubber green top sodium heparin tubes unless pregnant then draw only 2 tubes)
 - CBC (to be performed in UAMS clinical laboratory)
 - CMP (to be performed in UAMS clinical laboratory)
- Have the subject fill out "12-Month Visit Questionnaire" during the visit

6.9.2 Follow-Up to the 12-Month Visit

The Study Coordinator and Principal Investigator or Co-Investigator will review all information and test results from the 12-Month Visit and schedule any optional follow-up visits as soon as possible following this visit.

- If no evidence of HSIL upon biopsy, the subject will complete the study.
- If persistent HSIL is present, the subject may choose either to (1) have LEEP performed as a part of the study or (2) complete the study and be followed by a gynecologist.
- If a cervical cancer diagnosis is confirmed prior to being withdrawn from the study, the subject may be offered a hysterectomy if a study physician determines it to be medically necessary.

6.10 OPTIONAL LEEP VISIT

6.10.1 Procedures for LEEP Visit

- Blood may be drawn from some subjects as explained above:
 - Immunomonitoring and other analyses (eight 10.0 mL rubber green top sodium heparin tubes)
 - CBC, CMP or other tests as needed (to be performed in UAMS clinical laboratory)
- Perform LEEP biopsy
 - ThinPrep specimen for HPV-DNA and bacterial testing may be obtained
 - Excise visible lesion or, if no visible lesion seen, excise from an area where biopsies positive for HSIL were obtained at the 12-Month Visit
 - LEEP may be performed in the OR if medically necessary A COVID-19 test will be required per hospital policy prior to intervention in the OR.

- If a cervical cancer diagnosis is confirmed prior to being withdrawn from the study, the subject may be offered a hysterectomy if a study physician determines it to be medically necessary.

6.10.2 Follow-Up to the LEEP Visit

The study coordinator will contact the subject and review the LEEP biopsy results (after examined and signed out by hospital pathologist on service) (Record in CRF). In the event of inconclusive LEEP results, a repeat LEEP will be offered if a study physician determines it to be medically necessary. Additional follow-up visits will be scheduled as necessary. Blood may be drawn from some subjects as explained above for immunomonitoring and other analyses (eight 10.0 mL rubber green top sodium heparin tubes).

6.11 OPTIONAL FOLLOW-UP VISITS

6.11.1 When Optional Follow-Up Visits should be scheduled

Since a majority would prefer to receive test results and to have the follow-up plan explained over the phone, most subjects will not be scheduled for a follow-up visit after a screening visit. It would be common to schedule a follow-up visit after an Optional LEEP Visit since a gynecologist may need to examine recovery after LEEP. In rare instances, if a diagnosis of invasive cervical cancer is confirmed, a hysterectomy may be offered if a study physician determines it to be medically necessary prior to withdrawing the subject from the study. Follow-up visits can be scheduled:

- After being informed that the subject is not eligible for vaccinations
- Anytime during study participation
- After completing the Optional LEEP Visit
- After exiting the study without completing all the visits
- For evaluation of AEs
- To obtain contraceptives including:
 - Oral contraceptive pick up
 - Depo Provera injections
 - Placement/removal of IUD
- For diagnostic purposes and surgical intervention deemed medically necessary during the subjects' study participation, including but not limited to, colposcopy or LEEP performed in the OR, hysterectomy due to invasive cervical cancer, cone biopsy or medical imaging such as ultrasound, computed tomography (CT) scan, or magnetic resonance imaging (MRI) scan.
 - Surgical intervention required after the subject's study participation has ended will be the responsibility of the subject.
 - For any procedures performed in the OR, a COVID-19 test may be required per hospital policy prior to intervention. The study will cover the cost of mandatory pre-operative COVID-19 testing while institutional COVID-19 precautions are in effect.

6.11.2 Procedure at the Follow-Up Visit

- Gynecologists may perform a pelvic examination if indicated.
- The study coordinator, a clinic nurse, a study nurse, or one of the investigators may explain the subject's condition
- Directions for following up on the condition may be provided
- Blood may be drawn from some subjects as explained above for:

- Immunomonitoring and other analyses (eight 10.0 mL rubber green top sodium heparin tubes)
- CBC, CMP or other tests for evaluation of the AEs as needed (to be performed in UAMS clinical laboratory)

6.12 IF THE SUBJECT DID NOT COMPLETE THE STUDY

Subjects may not complete the study for a variety of reasons including serious toxicity, non-compliance, lost to follow-up, etc. In these instances, and for subjects who completed at least one vaccination visit, the study coordinator will ensure that subjects complete the “Early Termination Questionnaire” over the phone, via e-mail, or by mail (no stamp will be provided).

7 SUBJECT COMPENSATION

7.1 COMPLETERS AND NON-COMPLETERS, TRAVEL STIPENDS AND ANNUAL LIMITS

7.1.1 Subjects Who Complete the Study

A check or gift cards for \$300 will be mailed after the completion of the study (after the 12-Month Visit) to a mailing address provided by the subject.

7.1.2 Subjects Who Do Not Complete the Study

- If a subject is withdrawn due to vaccine-related toxicity (see stopping rules), due to becoming pregnant because contraception failure, or in cases of advancing disease after at least one completed vaccination visit, a check in the amount of \$300 will be mailed to an address provided by the subject once the “Early Termination Questionnaire” has been completed.
- For subjects who terminated early but not because of toxicity or due to non-compliance including cases of consequent pregnancies, \$50 per visit for each of Visits 1-4, the 6-Month Visit, and 12-Month Visit completed will be mailed if the subject completes the “Early Termination Questionnaire”. No compensation will be provided for the Screening Visit, Optional Follow-Up Visit(s), and Optional LEEP Visit.

7.1.3 Travel Stipends

- For subjects travelling more than 50 miles one-way to come for appointments, pre-visit travel stipends will be available.
- Stipends will be calculated and verified (by study staff) based on mileage from point of origin to the appointment location using internet mapping software, such as Google Maps or MapQuest.
- Stipends will be provided in the form of a pre-loaded gift card.
- Stipend amounts:
 - \$40 per visit for those travelling > 50 miles but < 100 miles
 - \$60 per visit for those travelling ≥ 100 miles but < 150 miles
 - \$80 per visit for those travelling ≥ 150 miles but < 200 miles
 - \$100 per visit for those travelling ≥ 200 miles

7.1.4 Annual Limit on Gift Cards

The maximum amount of gift cards that can be dispensed to each subject is \$600 per calendar year. If more than \$600 is owed to a subject (very unlikely to ever happen), the amount exceeding \$600 will be paid in the next calendar year.

8 OUTCOME MEASURES

8.1 CLINICAL ASSESSMENTS (UAMS Pathology Laboratory)

Clinical response will be assessed (by Pathologists on service in the Pathology Department) by comparing punch biopsy results from screening (having had HSIL is the inclusion criterion) with the quadrant biopsies performed at the 12-Month visit. The result of the highest grade will be recorded. The subject will be considered a “complete responder” if the 12-Month quadrant biopsies are negative for CIN, a “partial responder” if the show show CIN 1 or a “non-responder” if the biopsy shows HSIL (CIN 2 and/or 3). In addition to the above analysis of subjects who exited after the 12-Month Visit, another analysis may be performed with addition of subjects who exited the study after the 6-Month Visit if histological results (biopsy and/or LEEP) are available at 6 months.

8.2 VIROLOGICAL STUDY (HPV-DNA TESTING ([name] Laboratory) AND BACTERIAL TESTING (University of Chicago Argonne Laboratory))

The ThinPrep samples will be tested for the presence of HPV-DNA. A commercially available kit such as the “Linear Array HPV Genotyping Test” may be used (Roche Molecular Diagnostics, Inc., Alameda, CA). This kit tests for 37 HPV types (6, 11, 16, 18, 26, 31, 33, 35, 39, 40, 42, 45, 51, 52, 53, 54, 55, 56, 58, 59, 61, 62, 64, 66, 67, 68, 69, 70, 71, 72, 73, 81, 82, 83, 84, IS39, and CP6108). The human β -globin signal will also be assayed as a positive control for sample adequacy for DNA content from each sample. Positive-control samples (with added HPV plasmid DNA and plasmid-encoded human β -globin gene) and negative-control samples (no HPV plasmid DNA and no human β -globin gene) will be provided by the manufacturer and will be included in each experiment. HPV types 31, 33, 35, 52, 58, and 67 will be considered “HPV 16-Related”, additionally HPV types 18, 39, 45, 51, 53, 56, 59, 66, 68, 69, 70, 73, and 82 will be considered “High Risk”, and types 6, 11, 40, 42, 54, 61, 62, 71, 72, 81, 83, 84, and CP6108 will be considered “Low Risk” [58]. If samples are still available after HPV testing, other gene sequencing and gene expression studies may be performed for subjects who agreed in the consent for future use of remaining samples.

The virological response will be assessed by comparing HPV-DNA testing results before and after vaccination. The subject will be considered a “clearer” if at least one HPV type(s) present before vaccination becomes undetectable at both 6-Month and 12-Month Visits. Otherwise, a subject will be considered a “persistor” as long as at least one HPV type was detected at baseline.

The ThinPrep samples will also be 16S rRNA DNA tested to assess the nature and the diversity of the cervical microbial community. A commercially available Vaginal Microbiome Genome Mix will be used as a positive control, and a liquid in ThinPrep without cervical sampling will be used as a negative control. Illumina MiSeq platform will be used for sequencing. The presence and abundance of microbiome at the species to phylum levels will be correlated with the vaccine response and other immunological parameters.

8.3 IMMUNOLOGICAL ASSESSMENTS

8.3.1 ELISPOT Assay ([name] Laboratory)

An immune assay such as an ELISPOT assay to assess the presence of HPV-specific T-cells will be performed. After each blood draw, PBMCs will be separated into CD14+ and CD14- populations and cryopreserved. To eliminate interassay variability, all three blood samples (before vaccination, after two vaccinations, and after four vaccinations) will be used to establish T-cell lines and to perform ELISPOT assays. CD3 T-cell lines will be established by stimulating in vitro magnetically selected CD3 cells with autologous mature dendritic cells exposed to HPV 16 E6-vac and E6-GST. ELISPOT assays will be performed as previously described [28]. We typically examine 10 regions within the HPV 16 E6 protein (E6 1–25, E6 16–40, E6 31–55, E6 46–70, E6 61–85, E6 76–100, E6 91–115, E6 106–130, E6 121–145, and E6 136–158). The assay will be performed in triplicate if sufficient cells are available. In order to compare each region before vaccination and after 2 or 4 injections, a t test for paired samples will be performed, as described previously [59]. Therefore, each subject will be assessed in terms of the number of regions with statistically significant increased T-cell responses after two injections or four injections determined by using Student's paired t-test. Remaining CD3 T-cells may be used to assess the recognition of homologous epitopes from other high-risk HPV types, to describe novel epitopes, and/or to assess the endogenous processing of such epitopes.

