1.4.6 Immunological response

1.4.6.1 Systemic

Immunological responses to HPV-16 E6, as measured by IFN- γ ELISPOT assay, were similar among the first 3 dose levels in terms of detecting positive response to at least one new E6 region and for the increase in response being statistically significant (**Table 3**). The lowest response rate was observed in the 500- μ g dose level. No immunodominant HPV-16 E6 region was identified and the number of regions to which new immune responses were detected was also variable (**Fig. 3**).

Immune profiling (**Fig. 4**, upper panel) showed statistically significant increases in circulating Th1 cells after 2 ($p=0.02$) and 4 vaccinations ($p=0.0004$). Th2 cells initially increased significantly ($p=0.01$) but decreased to below baseline level after 4 vaccinations, although not significantly. Treg levels were minimally changed. The differences in Treg levels prevaccination ($p=0.03$) and post-2 vaccinations ($p=0.04$) between these two groups were statistically significant (**Fig. 4**, lower panel).

Fig. 3 HPV 16 E6- and E7-specific CD3 T-cell responses before vaccinations, after 2 vaccinations, and after 4 vaccinations. T-cell lines were established by stimulating CD3 T-cells with autologous dendritic cells pulsed with HPV 16 E6-vac, E6-GST, E7-vac, and E7-GST. Samples from different visits were tested with overlapping peptides in the same ELISPOT assay, and each region was tested in triplicate. Results are shown for subjects with statistically significant increases to the E6 peptides, and the regions with significant increases (paired *t*-test) are marked by “*”. Subjects 4 and 11 also had a significant increase to E7 (marked by “e”), which may represent the first examples of

[figure not shown]

Table 3. Summary of results from the dose-escalation Phase I clinical trial

Characteristics\Dosage (n)	50 µg (14)	100 µg (6)	250 µg (6)	500 µg (5)	All (31)
Histological regression, % (n)					
Responders	50 (7)	50 (3)	33 (2)	40 (2)	45 (14)
Virological response ^{a,b} , % (n)					
Responders	85 (11)	50 (3)	50 (3)	40 (2)	70 (21)
Immunological response, % (n)					
New response ^c to HPV-16 E6	64 (9)	67 (4)	83 (5)	20 (1)	61 (19)
Significant response ^d to HPV-16 E6	43 (6)	50 (3)	50 (3)	20 (1)	42 (13)

[figure not shown]
a At least one HPV type detected at entry became undetectable at exit

b One subject had no HPV detected at entry in the 50 µg group

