c New response was detected after vaccination but not prior to initiation of vaccination

d Significant response had $p < 0.05$ using Student's *t*-test comparing values before and after vaccination

[figure not shown]
Fig. 4 FACS analysis of peripheral immune cells. The upper panel show systemic Th1, Th2, and Treg before, after 2, and after 4 vaccinations. In the lower panel, responders are indicated by filled circles while non-responders are indicated by filled squares. None of the subjects with prevaccination Treg levels $\geq 0.7\%$ was a vaccine responder. Cells were first stained with antibodies for surface markers CD3, CD4, and CD25. Staining for intracellular T-bet, GATA3, and Foxp3 was performed with the Foxp3 staining kit according to the manufacturer's instructions (eBioscience). Th1 cells were expressed as a percentage of CD4 cells positive for T-bet, Th2 cells as a percentage of CD4 cells positive for GATA3, and Treg cells as a percentage of CD4 cells positive for CD25 and Foxp3. Paired *t*-test (upper panel) or Wilcoxon rank-sum test (lower panel) was used.

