9.3 ASSESSING IMMUNOLOGICAL RESPONSE AND VIRAL CLEARANCE

9.3.1 Immunological Response

9.3.1.1 CD3 T-Cell Response to HPV

As described above, a paired t-test for paired samples will be performed in order to compare each region with increased positivity index after 2 or 4 injections compared to pre-vaccination, as shown in Fig. 3 for the PepCan arm. An analogous analysis will be performed for the Candin® arm, and the number of regions with statistically significant increases will be compared between the two treatment arms to elucidate the additive effects of the E6 peptides.

A correlation between CD3 T-cell response to HPV and clinical response will be examined by drawing a contingency table for a number of subjects with at least one region with statistically significant increase to E6 in "responders" and "non-responders" separately for the PepCan and Candin® groups. Fisher's exact test will be used.

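### The per-region T-cell test is a paired t-test on replicate wells, but the protocol states no link between a before well and an after well; unless one exists, the verdict depends on well order and power is lost

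*Protocol*

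**What the plan says.** Protocol Section 8.3.1 (ELISPOT Assay) sets the layout: "The assay will be performed in triplicate if sufficient cells are available". About ten regions of the E6 protein are examined. For the source of the cells it says that "all three blood samples (before vaccination, after two vaccinations, and after four vaccinations) will be used to establish T-cell lines". The test is given as "In order to compare each region before vaccination and after 2 or 4 injections, a t test for paired samples will be performed", with a reference to an earlier paper (reference 59) for the method. The result is used so that "each subject will be assessed in terms of the number of regions with statistically significant increased T-cell responses after two injections or four injections".

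Section 9.3.1.1 repeats the test on a named scale: "a paired t-test for paired samples will be performed in order to compare each region with increased positivity index after 2 or 4 injections". The region verdicts then feed two analyses. The number of significant regions is compared between PepCan and Candin®, to show what the E6 peptides add. Within each arm, women with at least one significant region are cross-tabulated against histological response by Fisher's exact test.

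The Phase I legend to Fig. 3 (Section 1.4.6.1) describes the same set-up: "Samples from different visits were tested with overlapping peptides in the same ELISPOT assay, and each region was tested in triplicate". That legend names a paired t-test, while the footnote to Table 3 speaks only of Student's t-test at the 0.05 level. The SAP has no ELISPOT analysis.

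**The concern.** A paired test is right when each before value has its own partner among the after values. Here the woman links the two sets of wells as a whole. Nothing stated in the protocol links before well 1 to after well 1 rather than to after well 2 or 3. If no such link exists, three before wells and three after wells can be paired in six ways with equal justification, and the p-value changes with the choice. The test also spends half of its degrees of freedom on a pairing that removes no variance.

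At stake is the label of T-cell responder, both per region and per woman. With about 40 women per arm, a label that is partly arbitrary and misses real rises would tend to blur the comparison between arms and the comparison of T-cell response with regression.

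**Working it through.** **Unit of analysis.** A count of significant regions for each woman needs a p-value for each woman and region. Pairing across women cannot give that, so the data for one test are the replicate wells: n = 3 before and n = 3 after.

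**Inputs.** Three wells per region and visit (Section 8.3.1). Level 0.05 (Phase I, Table 3 footnote). Sidedness is not stated, so two-sided is assumed. The protocol gives no well standard deviation (SD), effect size or power for this assay. There is thus no stated figure to reproduce, and the rise d, in well SDs, is shown over a range. Wells are taken as independent and normal.

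**Formulas.** The paired test has n − 1 = 2 degrees of freedom, critical t 4.303. The two-sample test has 2(n − 1) = 4, critical t 2.776. With independent wells both have the same noncentrality, d × √(3/2). At d = 3 this is 3 × 1.2247 = 3.67.

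**Power from the noncentral t distribution.**

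| Rise d (well SDs) | Paired, 2 df | Two-sample, 4 df |
|---|---|---|
| 2 | 29% | 46% |
| 3 | 51% | 78% |
| 4 | 71% | 95% |
| 6 | 93% | 99.9% |

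The rise needed for 80% power is 4.6 well SDs paired and 3.1 two-sample. At one-sided 0.05 the gap is smaller: 49% against 65% at d = 2, and 75% against 91% at d = 3.

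**Dependence on order.** Take illustrative wells 20, 24, 28 before and 32, 36, 41 after. The mean difference is 37/3 = 12.33 under every pairing.
- Matched in ascending order, the differences are 12, 12, 13 (SD 0.577), so t = 12.33 / (0.577/√3) = 37.0 and p = 0.0007.
- With the after wells reversed, the differences are 21, 12, 4 (SD 8.50), so t = 2.51 and p = 0.129.
- The other four orders give p = 0.034, 0.042, 0.098 and 0.105.
- The two-sample test on the same six wells gives t = 3.54 and p = 0.024, whatever the order.

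In 100,000 simulated data sets, the verdict differed among the six orders in 56% at d = 2, 62% at d = 3 and 51% at d = 4.

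**If a real pairing exists.** With correlation ρ between paired wells, the paired noncentrality becomes d × √(3 / (2(1 − ρ))). At d = 3 and ρ = 0.6 this is 5.81, and power is 82%, equal to the two-sample test on the same wells (82%). At ρ = 0.7 it is 89% paired against 83% two-sample.

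**Error rate with no change.** With one order fixed in advance, upward calls are 2.5% for either test.

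**Line-to-line variation.** Wells replicate one T-cell line per visit. Suppose there is no vaccine effect, and each line's mean varies with an SD equal to one well SD (assumed). Upward calls are then about 8% paired and 12% two-sample. At two well SDs they are about 18% and 24%.

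**The case against.** The strongest reply is that an unstated pairing is not an absent one. The protocol refers to reference 59 for the test and to an earlier paper for the assay, and neither could be read here. The Phase I legend says that visits were run in the same assay. If the plates were laid out so that a before well and an after well share a row or other block, pairing could be as good as the two-sample test or better. This stands. A reader might infer that the wells are known to be unpaired, but the documents show only that no link is stated.

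A reader might also infer an inflated false-positive rate. Some order among the six shows a significant increase in 8.9% of unchanged regions, but reaching that figure requires choosing the order after seeing the data, and nothing in the protocol suggests this. Nor do the documents say what is done when cells are too few for triplicates. With duplicates the paired test would have 1 degree of freedom (critical t 12.71), but that case is an assumption.

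Two further points stand. The power gap depends on effect sizes that the protocol does not give, and it is small above about 6 well SDs. A more sensitive well-level test also picks up more differences between lines that have nothing to do with vaccination. It does not settle multiplicity over ten regions either.

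The reply does not remove the need to say what forms a pair. As written, an analyst holding six wells cannot tell which of six p-values is the planned one.

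**Conclusion.** The point holds conditionally. The plan prescribes a paired test within a woman and region without defining the pairs. Unless a real block links the wells, the region verdict depends on arbitrary order, and power is lower by 17 points at a rise of 2 well SDs (46 − 29), 27 at 3 (78 − 51) and 24 at 4 (95 − 71). These figures assume independent normal wells, triplicates and two-sided 0.05. At a rise of 3 SDs the gap closes at a true well correlation of about 0.6.

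The reach is limited to the tertiary immunological analyses in Section 9.3.1.1. A reader might carry the concern over to the efficacy result, but the primary histological comparisons and the safety tables do not use this test.

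**What to change.** In Sections 8.3.1 and 9.3.1.1, replace the paired t-test by a two-sample t-test on the replicate wells of the same region, before against after. Keep the positivity index that Section 9.3.1.1 names, referenced to background, and add its definition, which the protocol lacks. Raw spot counts would not do: a rise in background between two separately grown lines could then pass for an E6 response. Preferably pool the well variance within each woman. With ten regions, three samples and triplicates this gives 10 × 3 × 2 = 60 degrees of freedom, provided that the well variance is similar across regions on the chosen scale. State the sidedness. Keep the paired result as a bridge to Phase I. Retain pairing as the main test only if the protocol names the block that defines each pair and fixes it before the plates are read.

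The cost is wording and code; the wells and the assay do not change. Region counts will no longer be computed exactly as in Phase I. Because the two-sample test also responds more to differences between lines, significant regions should not be read as vaccine effects without the comparison between arms.
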